#### 13.5. BAILOUT STENTING OF TARGET LESION (POST-STUDY DEVICE)

The use of a bailout stent may occur in the event of persistent flow-limiting dissection not able to be treated with the Tack implant (or as otherwise required for safety of the subject). All enrolled subjects in whom at least one Tack implant is placed and receive a bailout stent to any deployed Tack within the target lesion will be followed for the duration of the study. Details around the use of a bailout stent will be captured in the eCRF including but not limited to; name/manufacturer, reason for stenting, length diameter, ruler and vessel location(s).

## 14. POST-PROCEDURE/PRE-DISCHARGE

All subjects will be assessed prior to discharge (Pre-Discharge) and shall receive a medical regimen for the medications required post-procedure per **Table 9** “Recommended Study Medications” in **Section 12**. All concomitant medications (antiplatelet/anticoagulant) shall be captured in the eCRF.

### 14.1. REQUIRED ASSESSMENTS

Assessments required at pre-discharge include the following:

- Adverse event occurrence
- Study medication assessment (antiplatelet agents/anticoagulants)

All subjects receiving treatment with a Tack implant should be provided with the Tack Endovascular System Patient Implant Card (PIC). The PIC is designed for the patient to carry along with their insurance cards. This PIC is to be completed by the designated research personnel to include information pertaining to the Tack device(s) including the model, lot number and vessel location of the implanted Tack(s) and the date of the index procedure. The card also provides manufacturing information and MRI Compatibility.

## 15. REQUIRED FOLLOW-UP VISITS AND ASSESSMENTS

All subjects will be required to return for clinic follow-up visits as outlined in **Table 8** of **Section 8.1** and in the sections below.

### 15.1. 30-DAY FOLLOW-UP VISIT (-2 DAYS / +14 DAYS POST-INDEX PROCEDURE)

The following assessments are required to be performed at the 30-day follow-up visit:

- Rutherford Classification
- Wifi Classification
- Wound Assessment
- Target limb resting ABI
- Target limb resting TBI
- Target Limb TcPO2 (if ABI, ankle pressure or toe pressure cannot be acquired)
- Duplex ultrasound (DUS)
- EQ-5D-3L
- Walking Impairment Questionnaire (WIQ)
- Adverse event occurrence
- Review of study medications (antiplatelets/anticoagulants)

### 15.2. 6-MONTH FOLLOW-UP VISIT (±30 DAYS POST-INDEX PROCEDURE)

The following assessments are required to be performed at the 6-month follow-up visit:

- Rutherford Classification
- Wifi Classification

- Wound Assessment
- Target limb resting ABI
- Target limb resting TBI
- TcPO2 (if ABI, ankle pressure or toe pressure cannot be acquired)
- Duplex ultrasound (DUS)
- EQ-5D-3L
- Walking Impairment Questionnaire (WIQ)
- Adverse event occurrence
- Review of study medications (antiplatelet agents/anticoagulants)

### 15.3. 12-MONTH FOLLOW-UP VISIT (±30 DAYS POST-INDEX PROCEDURE)

The following assessments are required to be performed at the 12-month follow-up visit:

- Rutherford Classification
- Wifi Classification
- Wound Assessment
- Target limb resting ABI
- Target limb resting TBI
- TcPO2 (if ABI, ankle pressure or toe pressure cannot be acquired)
- Duplex ultrasound (DUS)
- X-Ray assessment

**Note:** If an X-ray of all Tack implant(s) is performed before the 12-month visit and is within the 12-month visit window, this may be used in lieu of the x-ray required at the 12-month visit.

- EQ-5D-3L
- Walking Impairment Questionnaire (WIQ)
- Adverse event occurrence
- Review of study medications (antiplatelet agents/anticoagulants)

### 15.4. 24-MONTH FOLLOW-UP VISIT (±30 DAYS POST-INDEX PROCEDURE)

The following assessments are required to be performed at the 24-month follow-up visit:

- Rutherford Classification
- Wifi Classification
- Wound Assessment
- Target limb resting ABI
- Target limb resting TBI

- TcPO2 (if ABI, ankle pressure or toe pressure cannot be acquired)
- EQ-5D-3L
- Walking Impairment Questionnaire (WIQ)
- Adverse event occurrence
- Review of study medications (antiplatelet agents/anticoagulants)

15.5. 36-MONTH FOLLOW-UP VISIT (±30 DAYS POST-INDEX PROCEDURE)

The following assessments are required to be performed at the 36-month follow-up visit:

- Rutherford Classification
- Wifi Classification
- Wound Assessment
- Target limb resting ABI
- Target limb resting TBI
- TcPO2 (if ABI, ankle pressure or toe pressure cannot be acquired)
- EQ-5D-3L
- Walking Impairment Questionnaire (WIQ)
- Adverse event occurrence
- Review of study medications (antiplatelet agents/anticoagulants)

15.6. UNSCHEDULED TARGET LIMB ANGIOGRAPHY/REVASCLARIZATION

If a subject presents between study-required follow-up visits for an intervention to the target limb, the assessments below should be performed prior to the interventional procedure. In addition, all imaging studies performed should follow the guidelines set forth by the respective core laboratory. This imaging should be submitted to the respective core laboratories within 3 business days for review and analysis.

- Rutherford Classification
- Wifi Classification
- Wound Assessment
- Target limb resting ABI
- Target limb resting TBI
- TcPO2 (if ABI, ankle pressure or toe pressure cannot be acquired)
- Duplex ultrasound (DUS) (if clinically indicated)
- X-Ray assessment (if clinically indicated)

**Note:** If an X-ray of all Tack implant(s) is performed before the 12-month visit and is within the 12-month visit window, this may be used in lieu of the x-ray required at the 12-month visit.

- EQ-5D-3L
- Walking Impairment Questionnaire (WIQ)
- Review of study medications (antiplatelet agents/anticoagulants)

**Note:** Any change in study medication, including any loading dose provided during the unscheduled procedure, should be recorded in the eCRF.

#### 15.7. FOLLOW-UP VISIT COMPLIANCE

As part of the informed consent process, all reasonable efforts will be made to obtain complete data for all subjects according to the follow-up visit schedule. Investigators and research staff will be expected to maintain continuous and open communication with study subjects regarding their participation in this study.

Three attempts via telephone will be made to contact subjects who do not present for a study follow-up visit. If after three telephone attempts the subjects cannot be contacted, a certified letter should be sent by the PI or designated study coordinator to the subject's last known address. If possible, public records should be searched to ascertain survival status. If efforts to reach the subject are unsuccessful after three telephone contacts and a certified letter, and there is no evidence of subject expiration, or the site has not been notified of a subject's wish to withdraw consent, a Protocol Deviation for a visit not done must be documented in the EDC. A detailed record of all contact attempts should be maintained in the subject's file. This process should be repeated for every subsequent follow-up visits and documented accordingly. After required contact attempts are unsuccessful for at least 2 consecutive visits and the 12-month visit window (or any later subsequent visit window) has passed, only then should a subject be considered lost-to-follow-up (LTFU) and exited from the study.

#### 15.8. SUBJECT DISCONTINUATION AND REPLACEMENT

A subject may discontinue participation at any time without penalty or loss of benefits to which the subject is otherwise entitled. In addition, a subject may be discontinued if in the investigator's opinion it is in the subject's best interest. If a subject prematurely discontinues from the study, the reason will be recorded in the eCRF with supporting documentation. These results will be tabulated by number and percent for each category for discontinuation.

Subjects who prematurely exit the study after treatment will have their data maintained and evaluated up until the time of withdrawal. Subjects who are voluntarily or involuntarily (per PI discretion or if LTFU) withdrawn cannot re-enter the study. These subjects will not be replaced.

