#### 13.3.1. ENROLLMENT (INTENT-TO-TREAT)

A subject is defined as an intent-to-treat (ITT) and officially enrolled in the study once the Tack Endovascular System is advanced through the introducer sheath. Subjects in whom at

least one Tack implant is not placed, will be exited after 30 days. Subjects in whom at least one Tack implant is placed will be followed for 36 months.

In addition, the per-protocol (PP) population will be defined as ITT subjects with evaluable data that have met the definition for device success, excluding subjects with major deviations such as:

- A major inclusion/exclusion criterion deviation; or
- A major procedural deviation

The criteria for deviations meeting the classification of “major” will be defined by an independent designee before study endpoint data is available for statistical analysis.

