## 19. STATISTICAL METHODS AND CONSIDERATIONS

### 19.1. STUDY DESIGN

This is a prospective, multi-center, single-arm, non-blinded study designed to investigate the safety and efficacy of the Tack Endovascular System.

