#### 19.6. SAMPLE SIZE

The sample size for the primary efficacy endpoint of freedom from MALE at 6 months plus POD at 30 days was calculated using a one-sided, single group, normal approximation test of a proportion (with continuity correction) against a performance goal. The performance goal for this endpoint is 74% developed based on the information reported in table VIIb and figure 2A of Conte (2009). From figure 2A, the estimated 6-month rate of freedom from MALE + POD in the infra-popliteal group is 80.5% with 95% confidence interval calculated to be (77%, 84%). Applying the recommended 3% margin to the lower bound of the confidence interval yields the 74% OPG. Assuming the observed freedom from MALE+POD is 84% and a one-sided Type I error rate of 0.025, a sample size of 186 subjects provides 90% power to detect this difference between observed freedom from MALE+POD and the performance goal of 74%.

The sample size for the primary safety endpoint of MALE+POD at 30 days was calculated using the exact binomial distribution. This is also a one-sided, single group test of a proportion against a performance goal. The performance goal for this endpoint was established at 12%. This performance goal was derived from the information reported in table VIIa of Conte (2009). In that table, MALE+POD was not reported, however MALE and 30-day death were reported separately. The sum of those two estimates (8.9%) was used for sample size calculation. Conte (2009) established performance goals for safety endpoints by constructing a 95% confidence interval and using the upper bound of that interval as the performance goal. With some algebraic manipulation, a similar 95% confidence interval was established for the 8.9% point estimate of 30day MALE+POD which resulted in an upper bound of 11.9%. Therefore 12% is used as the performance goal for this endpoint. Assuming an observed MALE+POD rate of 5%

 Joseph L. Mills, Sr, MD, [name], David G. Armstrong, DPM, MD, PhD, [name], [name], [name], MPH, and [name], on behalf of the Society for Vascular Surgery Lower Extremity Guidelines Committee, The Society for Vascular Surgery Lower Extremity Threatened Limb Classification System: Risk stratification based on Wound, Ischemia, and foot Infection (WIFI). J Vasc Surg. 2014; Volume 59, Issue 1, Pages 220–234.e2

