#### 19.11. HANDLING OF MISSING DATA

For the primary analysis, only complete data will be used. Data will be considered “complete” if the subject had the event of interest at or prior to the time point for analysis and/or if the subject’s status is known at any time beyond the analysis window. Subjects without sufficient follow-up based on the lower end of the visit window will be excluded from the analysis (that is, subjects must have at least 28 days of follow-up for the 30 day endpoints, 6 months minus 30 days for the 6 month endpoints and 12 months minus 30 days for endpoints defined at 1 year). Thus, subjects without events but whom are known to be event free at a later visit will have their data imputed backward but not forward for the primary analysis.

As a sensitivity analysis, missing values for the primary endpoints will be replaced by regression imputations based on a multivariate logistic regression analysis of completed cases (those that have follow-up at the required time point or experienced the endpoint in question prior to final follow-up visit). Covariates to consider for inclusion in the logistic regression include but are not limited to: age, sex, history of hypertension, diabetes, previous peripheral vascular intervention, BMI, dissection location (mid popliteal (P2), distal popliteal (P3), tibioperoneal trunk, peroneal, anterior tibial, or posterior tibial), and baseline Rutherford class. Backward selection will be used to identify predictors. In the event there are no significant predictors in the logistic regression model at  $\alpha=0.1$ , a “hot deck” method will be employed where a random selection of the outcome from a group of completed cases with similar baseline characteristics will be used as the imputed value using simple random sampling with replacement. The baseline characteristics to be used for the hot deck method will include but are not limited to age ( $\neq$  median), sex, dissection location (mid popliteal (P2), distal popliteal (P3), tibioperoneal trunk, peroneal, anterior tibial, or posterior tibial), use of statin medication, current smoker status and baseline Rutherford class.

With either method of imputation, five complete datasets will be constructed. Each dataset will be analyzed separately and then combined in an overall analysis across the five complete datasets.

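### After an investigator-initiated exit the protocol requires no further limb or vital status, so a later MALE would go uncounted in the complete-case primary efficacy analysis

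*Combined protocol and SAP*

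**What the plan says.** **Exit (section 15.8).** Discontinuation may be the investigator's decision: "a subject may be discontinued if in the investigator's opinion it is in the subject's best interest". No qualifying reasons are listed. On data after exit: "Subjects who prematurely exit the study after treatment will have their data maintained and evaluated up until the time of withdrawal". On return: "Subjects who are voluntarily or involuntarily (per PI discretion or if LTFU) withdrawn cannot re-enter the study". The reason for exit is recorded with supporting documentation and tabulated.

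**Primary analysis (section 19.11).** "For the primary analysis, only complete data will be used". A subject with an event by the time point is complete, and so is one whose status is known later. Otherwise: "Subjects without sufficient follow-up based on the lower end of the visit window will be excluded from the analysis". For 6-month endpoints that lower end is 6 months minus 30 days. Section 19.8.2 says all ITT subjects are included, so 19.11 narrows that set.

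**Safeguards.** Section 19.11 adds regression or hot-deck imputation, and a tipping point analysis that runs from all missing subjects counted as successes to all counted as failures. Section 19.12 defines trial success by the two primary endpoints and mentions no sensitivity analysis.

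**Design.** Section 19.1 describes a "prospective, multi-center, single-arm, non-blinded study". For primary efficacy, section 19.6 says: "The performance goal for this endpoint is 74" percent.

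**The concern.** The study device is an implant placed at the index procedure. Ending participation later does not change exposure to it; what mainly ends is observation. The components of the primary endpoint (death to 30 days, above-ankle amputation, major re-intervention) can be learned by telephone or from records without a study visit.

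The investigator who decides on discontinuation is unblinded and can see how the limb is doing. If exits are more common among limbs that are doing badly, the remaining complete cases are a favourable selection. No control arm shares the distortion, because the comparison is with a fixed goal.

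The protocol treats missed visits differently. Under section 15.7 such a subject is pursued by telephone and certified letter. That subject can be declared lost only after two consecutive visits with failed contact and after the 12-month window has passed. Section 19.11 also allows event-free status at a later visit to be carried back. A subject discontinued by the investigator gets neither protection.

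At stake is the primary efficacy claim if the result falls close to the threshold.

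**Working it through.** **Inputs.** Goal 74%, design rate 84%, one-sided alpha 0.025, power 90%, 186 evaluable and 232 enrolled (section 19.6); continuity-corrected Z with the variance at the estimated proportion (section 19.8.2); complete-case rule (section 19.11). The number of informative exits is an assumption.

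**1. The plan's own figure.** Without continuity correction, n = [(1.960·√(0.74·0.26) + 1.282·√(0.84·0.16)) / 0.10]² = 176.8. With correction, (176.8/4)·[1 + √(1 + 2/(176.8·0.10))]² = 186.6, against 186 stated. Then 186/0.80 = 232.5, against 232 stated. The sample size is not in question.

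**2. Threshold at 186.** For p̂ above 0.74, Z = (p̂ − 0.74 − 1/(2n)) / √(p̂(1 − p̂)/n), and the test passes if Z > 1.960.

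- 148/186 = 79.6%: (0.0557 − 0.0027)/0.0296 = 1.79, fails.
- 149/186 = 80.1%: (0.0611 − 0.0027)/0.0293 = 1.99, passes.

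The smallest passing result is 149.

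**3. Effect of uncounted failures.** Removing a would-be failure lowers n and leaves the successes unchanged.

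| True result | Z | Failures uncounted | Analysed result | Z |
|---|---|---|---|---|
| 147/186 (79.0%) | 1.60, fails | 2 | 147/184 (79.9%) | 1.90, fails |
| 147/186 (79.0%) | 1.60, fails | 3 | 147/183 (80.3%) | 2.06, passes |
| 145/186 (78.0%) | 1.21, fails | 5 | 145/181 (80.1%) | 1.97, passes |
| 156/186 (83.9%, design rate) | 3.56, passes | 3 | 156/183 (85.2%) | 4.19, passes |

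**4. Type I error at a true rate of 74%.** Let a share w of failing subjects leave uncounted. The number removed is binomial(N, 0.26w). Given r removed, the successes are binomial(N − r, 0.74/(1 − 0.26w)). Summing the exact rejection probability of the same test gives:

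| w (assumed) | Expected uncounted, N = 232 | Type I error, N = 232 | Type I error, N = 186 |
|---|---|---|---|
| 0 | 0 | 0.025 | 0.032 |
| 2% | 1.2 | 0.037 | 0.036 |
| 5% | 3.0 | 0.058 | 0.052 |
| 10% | 6.0 | 0.108 | 0.098 |

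**5. What the tipping point analysis would show.** Take 147/183 with those 3 subjects as the only missing ones. The analysis runs from 150/186 down to 147/186. It loses significance at the second imputed failure (148/186), and its worst case is the true result.

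**The case against.** The strongest reply is that the plan already exposes the problem. The tipping point analysis bounds it, as step 5 shows, and imputation is added. A reader might infer that no analysis can deal with the bias. The documents do not support that: the events cannot be recovered, but their possible effect can be bounded and would be reported. What remains is that these analyses are supportive only, that the imputations draw on completed cases, and that section 19.12 does not refer to them.

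A reader might also see a contradiction with section 13.3.1, which says: "Subjects in whom at least one Tack implant is placed will be followed for 36 months". It is not one. That sentence gives the planned duration, and section 15.8 governs premature exit.

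Nor does section 15.8 forbid later collection; it requires none. Section 17 asks that reportable events be followed until resolved or stable, so a limb problem already reported as a serious adverse event may stay under observation. That section does not mention withdrawn subjects, so it reduces the gap without closing it. The consent pages were not available, and they may contain wording on follow-up after withdrawal.

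Three further points for the plan stand. Events before exit count as failures. Loss to follow-up, as section 15.7 defines it, cannot remove a subject before the 6-month endpoint, so the 20% allowance in section 19.6 is not an estimate of this kind of exit. The illustration also assumes that every such exit is a would-be failure; exits among subjects who would have stayed event-free push the estimate the other way.

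**Conclusion.** The point holds as a weakness in follow-up design. As written, the plan can lose primary endpoint failures after an investigator-initiated exit before 6 months minus 30 days, and the primary analysis then excludes those subjects. Nothing in the documents shows that this happened or was intended, and a deteriorating limb is not named as a reason for discontinuation.

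The effect is confined to results near the threshold: 3 uncounted failures turn a true 147/186 into a pass, and 5 do so for 145/186. At the design rate the conclusion does not change. Under the assumed shares of 2% to 10% of failing subjects lost this way, type I error with 232 subjects would be 0.037 to 0.108, against 0.025 with none lost. The documents give no rate of investigator-initiated exit, so these figures are a range of possibilities and not an estimate.

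A reader might extend the claim to limb salvage. Early exits could bias its Kaplan-Meier estimate through informative censoring, but section 19.13 attaches no hypothesis to it, so no pass or fail follows.

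**What to change.** In section 15.8, separate three things: stopping study visits and procedures, discontinuation by the investigator, and withdrawal of consent to data collection. Limit investigator-initiated discontinuation to visits and procedures (duplex ultrasound, X-ray, questionnaires).

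Unless the subject withdraws consent to data collection, continue to ascertain death, above-ankle target limb amputation and major re-intervention by telephone or medical records. Do this at least through the 6-month endpoint and preferably at each scheduled time point. Send the events to the CEC. State in section 19.11 that subjects whose status is known in this way are included in the primary analysis. When a subject asks to withdraw, ask for permission for this limited follow-up and record the answer.

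The cost is protocol and consent wording, a short status page in the eCRF, and a few telephone or record checks per discontinued subject. No extra visits or procedures are needed, and the subject's right to withdraw is untouched. Those who refuse all further data collection remain missing and are covered by the existing sensitivity analyses.

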### 16. RISK/BENEFIT ASSESSMENT

#### 16.1. RISKS

The use of the Tack Endovascular System in percutaneous transluminal balloon angioplasty (PTA) may result in anticipated potential risks or complications similar to other available endovascular implant devices (such as stents) used in PTA procedures. Such risks are included in the Tack Endovascular System Instructions for Use (IFU) and are listed below:

- Access failure or abrupt closure
- Allergic / anaphylactoid reaction to anticoagulant and/or antithrombotic therapy or contrast medium

- Allergic reaction to nitinol
- Amputation of lower extremity
- Anemia
- Angina / coronary ischemia / myocardial infarction
- Arrhythmia
- Arterial occlusion / (re) stenosis / dissection / thrombus
- Arterial spasm
- Arteriovenous fistula
- Blue toe syndrome
- Claudication or rest pain, worsened
- Death
- Disseminated intravascular coagulation
- Edema, peripheral
- Embolism
- Emergent repeat hospital intervention
- Fever
- Gangrene
- Gastrointestinal bleed from anticoagulation / antiplatelet medication
- Hematoma / hemorrhage
- Hypotension / hypertension
- Inadvertent venipuncture
- Infection / abscess at insertion site
- Inflammation
- Multi-organ failure
- Pain
- Pseudoaneurysm
- Renal insufficiency or failure
- Respiratory distress or failure
- Septicemia / bacteremia (sepsis)
- Tack implant embolization
- Tack implant migration (device moves over time)
- Tack implant occlusion / restenosis
- Tissue necrosis
- Trauma to adjacent structures
- Stroke / TIA (hemorrhagic / embolic)
- Vascular complications which may require surgical repair

These risks are present in any endovascular treatment procedure for which the study subjects would be indicated because of their disease and will be reviewed with all subjects during the informed consent process.

